## B. Adverse Events

Adverse events and SAEs will be documented on the “Adverse Event” eCRF page from the signing of the ICF until Follow-up/ Visit 10 or 28 days after the last dose of study treatment if subject is terminated early.

Treatment-Emergent AEs (TEAEs) is any condition that was not present prior to treatment with the study product but appeared following treatment, or was present at treatment initiation but worsened during treatment, or was present at treatment initiation but resolved and then reappeared while the individual was on treatment regardless of the intensity of the AE when the treatment was initiated. TEAE will be programmatically identified as AEs with an onset date on or after the first dose of study drug, and within 30 days after end of treatment.

When the AE start date is complete missing, adverse events will be assumed to be treatment-emergent. If AE start date is partially missing, please see AE data imputation in Section IV.D Missing Data, before determining TEAEs.

All adverse events will be coded according to MedDRA version 24.1.

Severity of AEs are graded as ‘Mild’, ‘Moderate’ and ‘Severe’. If the severity of the AE is missing it will be imputed as ‘Severe’ for analysis purposes. Relationship to study drug will be categorized for analysis purposes as ‘Related’ or ‘Not Related’. ‘Related’ include ‘Potentially Related’, ‘Probably Related’ and ‘Definitely Related’. AEs missing relationship status will be imputed as ‘Related’ in the related TEAE tables and listings.

An overall summary of number and percentage of subjects with at least one of the categories described below will be provided by treatment group and overall.

- Any AE
- Any TEAE
- Any TEAE of clinical interest
  - Malignancy
  - Major adverse cardiac events (MACE)
  - Tuberculosis (TB)
  - Inflammatory bowel disease (IBD)
  - Depression and suicidal ideation and behavior
  - Serious or opportunistic infection
  - Hypersensitivity reactions
- Any treatment-related TEAE
- Any serious TEAE
- Any serious treatment-related TEAE
- Any severe TEAE
- Any TEAE leading to study drug withdrawal
- Any treatment-related TEAE leading to study drug withdrawal
- Any TEAE leading to study drug interruption
- Any treatment-related TEAE leading to study drug interruption
- Any TEAE leading to death

The counts and percentages will be summarized for each PT and SOC by treatment group and overall. Additional summaries will also be provided by relationship to study drug and severity. A subject reporting multiple cases of the same TEAE will be counted once within

each system organ class, preferred term and will be counted once under the strongest relationship to study drug and worst severity.

- All TEAEs
- TEAEs with PT  $\geq 5\%$  in any treatment groups
- Treatment-related TEAE
- Serious TEAEs
- Serious treatment-related TEAEs
- TEAE leading to study drug withdrawal
- TEAE leading to study drug interruption
- TEAEs by strongest relationship to study drug
- TEAEs by worst severity

All AEs will be present in a by-subject listing. serious AEs, and TEAEs leading to study drug withdrawal will be present in separate listings.

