All safety analyses will be performed on the Safety Analysis Set. Adverse events will be coded using the Medical Dictionary for Regulatory Activities (MedDRA). Treatment-emergent adverse events (TEAEs) are defined as AEs that first occurred or worsened in severity after the first dose of study treatment. The AE summaries will be primarily based on TEAEs. Descriptive statistics for the number and percentage of subjects with TEAEs will be summarized by treatment arm, system organ class, and preferred term for all TEAEs, treatment-related TEAEs, serious TEAEs, and TEAEs leading to discontinuation of study treatment. All TEAEs will be further summarized by maximum severity and causality. All AEs will be present in a by-subject listing. Serious AEs, and TEAEs leading to discontinuation of study treatment will be present in separate listings.

No interim analysis for efficacy is planned.

Data Monitoring Committee:

There will be no independent Data Monitoring Committee for this study.

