- The causality assessment is one of the criteria used when determining regulatory reporting requirements.

Follow-up of AEs and SAEs

- The Investigator is obligated to perform or arrange for the conduct of supplemental measurements and/or evaluations as medically indicated or as requested by the Sponsor and/or designee to elucidate the nature and/or causality of the AE or SAE as fully as possible. This may include additional laboratory tests or investigations, histopathological examinations, or consultation with other health care professionals.
- If a subject dies during participation in the study or during a recognized follow-up period, the Investigator will provide the Sponsor and/or designee with a copy of any postmortem findings including histopathology.
- New or updated information will be recorded in the originally completed CRF.
- The Investigator will submit any updated SAE data to the Sponsor and/or designee within 24 hours of receipt of the information.

Reporting of SAEs

Safety Event Reporting to [REDACTED] via Paper CRF

• Email transmission of the paper Safety Event Report Form is the preferred method to transmit safety event information to [REDACTED] Safety with facsimile as a back-up method, if necessary.• Safety events should be reported to [REDACTED] at:
• [REDACTED]

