## II. Protocol Objectives and Study Endpoints

Objectives	Endpoints
Primary	

To evaluate the efficacy of RPT193 administered orally once daily (QD) for 16 weeks to subjects with moderate-to-severe AD.

	

% change in Eczema Area Severity Index (EASI) from baseline at Week 16.

To evaluate the safety and tolerability of RPT193 administered orally QD for 16 weeks.

	

Incidence of treatment-emergent adverse events.

Key Secondary	

 
To evaluate the efficacy of RPT193 administered orally QD for 16 weeks to subjects with moderate-to-severe AD.
 
	
 
% of subjects achieving a Validated Investigator Global Assessment (vIGA) score of 0 or 1 at Week 16.
 
% of subjects achieving EASI-75, defined as a 75% reduction in EASI from baseline to Week 16.
 

 
To evaluate the efficacy of RPT193 administered orally QD for 16 weeks to subjects with moderate-to-severe AD on subject reported symptoms associated with AD. Itch peak pruritus numerical rating scale (PP-NRS).
 
	
 
% change from baseline in PP-NRS from an itch daily e-Diary at Week 16.
 

Secondary	

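### The SAP's programmed TEAE flag leaves out the worsening part of its own definition, so a screening-onset AE that worsens on study drug and stays on its original record would be missing from the TEAE tables

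*SAP*

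**What the plan says.** SAP section II lists "Incidence of treatment-emergent adverse events" under the primary objectives. Section VII.B defines a TEAE in three parts. The first is a condition new after treatment, the second is one that "or was present at treatment initiation but worsened during treatment", and the third is one that was present, resolved and came back on treatment. Protocol 9.4.3 and Appendix 12 carry the same three parts. The protocol synopsis is shorter but keeps worsening: "AEs that first occurred or worsened in severity after the first dose of study treatment".

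The next sentence of SAP VII.B gives the derivation: "TEAE will be programmatically identified as AEs with an onset date on or after the first dose of study drug". The same sentence sets an upper limit on onset, 30 days after treatment ends. It has no test of severity. One supplementary rule follows: "When the AE start date is complete missing, adverse events will be assumed to be treatment-emergent". Partial start dates go to the imputation rules in SAP IV.D.

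AEs are recorded "from the signing of the ICF until Follow-up/ Visit 10 or 28 days after the last dose of study treatment" in subjects who terminate early, so AEs with onset before dosing are in the dataset. On follow-up of an existing AE, Protocol Appendix 12 says: "New or updated information will be recorded in the originally completed CRF". SAP I.C, which lists changes from the protocol, does not mention dropping the worsening part of the definition.

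**The concern.** The definition and the rule stand next to each other and do not agree. Programmers work from the rule, so the worsening part would be stated but not applied unless the way events are recorded happens to supply a post-dose onset date.

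The flag drives more than the headline incidence. In SAP VII.B it feeds the treatment-related, serious, severe, withdrawal, interruption and death rows and the tables by system organ class and preferred term. In VII.C it feeds the Kaplan-Meier analysis of time to first TEAE of clinical interest. Events missed in this way are, by definition, ones that got worse on study treatment.

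Outputs could also disagree. If such an event led a subject to stop treatment, the disposition table (SAP V.A) could show it as the reason while the table of TEAEs leading to withdrawal did not. The omission looks unintended, because the neighbouring rules lean toward counting: unknown onset is treated as treatment-emergent, missing severity as severe and missing causality as related.

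**Working it through.** The plan gives no figure to reproduce. The check applies the written definition and the programmed rule to each possible AE history.

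| AE history | Written definition | Programmed rule |
|---|---|---|
| New onset after first dose, within 30 days after end of treatment | TEAE | TEAE |
| Onset between consent and first dose, worsens on drug, kept on one record | TEAE | Not TEAE |
| Onset before first dose, resolves, returns on drug | TEAE | TEAE only if the recurrence is a new record with its own onset date |
| Medical-history condition that worsens on drug | TEAE | TEAE only if the exacerbation is entered as its own AE |
| Onset before first dose, no worsening | Not TEAE | Not TEAE |
| Start date completely missing | Cannot be judged | TEAE |

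The second row is a direct conflict. The third and fourth depend on how the site records the event.

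**Can the second row occur?** Yes. Collection starts at consent, and Protocol 6.0 allows up to 35 days of screening before first dose.

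**Do the documents give the worsening a new onset date?** Not expressly. Three statements in Protocol Appendix 12 bear on it:
- Exacerbation of a chronic or intermittent pre-existing condition meets the AE definition. This supports a separate record for some cases.
- Each event is to have its own entry. This does not say that worsening is a new event.
- Follow-up information goes on the original form. This suggests a single record but mentions neither severity nor onset date.

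The eCRF completion instructions, which would settle the matter, are not among the documents.

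**Size, on assumptions only.** Suppose 10% to 20% of subjects have an AE with pre-dose onset and 5% to 10% of those worsen on study without a new record. Neither rate comes from the documents.
- Low: 0.10 × 0.05 = 0.005, or 0.5% of subjects; 67 × 0.005 = 0.3 per arm.
- High: 0.20 × 0.10 = 0.02, or 2.0% of subjects; 67 × 0.02 = 1.3 per arm.

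If sites always open a new record at worsening, the number is zero.

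**The case against.** The best answer is that loss of events is conditional. A site that treats an exacerbation after first dose as a new AE gives it a post-dose onset, and the existing rule captures it. The Appendix 12 wording on pre-existing conditions and on separate entries can be read that way, and the follow-up sentence is general text that does not fix an onset date. This stands: a reader might infer that every screening-onset AE that worsens is excluded, and the documents do not support that. The clearest remaining case is an acute screening AE, still ongoing at first dose, that worsens and stays on one record.

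The second answer is that little disappears from view. SAP VII.B has an any-AE row, a listing of all AEs and a listing of serious AEs that is not limited to TEAEs. The counts of events of clinical interest in VII.C are, as worded, not limited to TEAEs either; only the Kaplan-Meier analysis is. Laboratory worsening shows in the shift tables of worst post-baseline grade (VII.D). This also stands. A reader might infer that events turning serious on drug would vanish from the report, but they would be missing only from the TEAE outputs.

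Third, the obvious washout event, a flare of atopic dermatitis, is generally not recorded as an AE under Appendix 12, and the eligibility criteria limit active infection and significant illness at baseline. TEAE incidence is summarised descriptively, and the rule is the same in every arm. These points limit the size and mean that no hypothesis test changes. They do not make the arms comparable on the missing events: if the drug aggravates existing conditions, the loss would be larger in the active arms.

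None of this reconciles the rule with the definition. If separate recording is what is meant to close the gap, the SAP should say so.

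**Conclusion.** The point holds as a mismatch between the stated TEAE definition and its derivation, on a primary safety endpoint. The affected events are those with onset between consent and first dose that worsen on study drug and remain on their original record. They would be left out of the TEAE tables and the time-to-first-TEAE analysis of clinical interest, and kept in the any-AE row and the listings.

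The size is unknown and probably small. The 0.3 to 1.3 subjects per arm rests wholly on assumed rates, and the true number depends on recording instructions that are not shown. The correction is worth making because it is cheap and because the events concerned are ones a safety reader would want counted.

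A reader might also infer that a pre-dose AE which becomes serious should be flagged on that ground alone. No TEAE definition in either document includes seriousness as a criterion, so that would need an amended definition and is not part of this correction.

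**What to change.** Do one of the following; either suffices provided the increase in severity is dated.

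1. Extend the flag in SAP VII.B: add AEs with onset before first dose that increase in severity on or after first dose and within the same window (up to 30 days after end of treatment). This needs a date for the severity change. The documents do not show whether the eCRF holds one.
2. Keep the onset rule, and state in the SAP and the CRF completion instructions that worsening after first dose is entered as a new AE record whose start date is the date of worsening. The existing rule then captures it. The same instruction should cover AEs that resolve and recur.

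Do not add a becoming-serious criterion unless the TEAE definition is amended as well.

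The first option costs one SAP sentence if the date is already collected. The second costs one SAP sentence, one CRF instruction and a check of screening AEs still ongoing at first dose. SAP I.B allows changes until treatment unblinding, so the choice should be made before the unblinded Week 16 analysis described in SAP IV.F. Neither option changes treatment, visits or the protocol's definition.

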### C. Adverse Events of Clinical Interest

A separate analysis focused on adverse events of clinical interest will also be performed. Adverse events of clinical interest are as follows and identified by the eCRF page "Adverse Events":

- Malignancy
- Major adverse cardiac events (MACE)
- Tuberculosis (TB)
- Inflammatory bowel disease (IBD)
- Depression and suicidal ideation and behavior
- Serious or opportunistic infection
- Hypersensitivity reactions

The counts and percentages will be summarized for each PT and SOC by treatment group and overall. Additional summaries will also be provided by strongest relationship to study drug and worst severity.

The time to first TEAE of clinical interest during the week 16 treatment period will be assessed by Kaplan-Meier estimates (K-M plot) by each AECI category. The time is defined as the date of first event – the date of first dose + 1. Subjects without an event will be censored at the last AE assessment date within the 16 week of treatment period.. Graphs of cumulative incidence rate over time will be presented by treatment group.

The adverse events of clinical interest will be present in a separate listing.

### D. Clinical Laboratory Test

All laboratory measurements include hematology, clinical chemistry, and urinalysis results, and will be converted to standard international (SI) units and US conventional units. Laboratory data will be summarized using descriptive statistics for the observed and change from baseline by treatment arm and overall. Worst post-baseline CTCAE grade shift from baseline tables will also be provided for hematology, clinical chemistry and urinalysis for lab test with available grading. Shift tables will be used to present the number and percentages of subjects with laboratory values within/outside normal reference ranges for parameters that do not have a CTCAE grading. Clinically significant changes will be reported as AE.

All laboratory data, including serology, pregnancy and other lab test, will be present in the listings. A by-subjects listing will also be provided for subjects with abnormal laboratory results.

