- Fasting required for labs at Baseline, Day 113 (Week 16), and Day 127/ET/Discon (Week 18). A subject should refrain from eating or drinking (except for water) for a period of at least 8 hours prior to the lab draw.
- FSH at Screening only for females of non-childbearing potential.
- The ACQ-5 instrument will only be assessed in subjects reporting a history of ongoing asthma at Screening.

- h. 
- i. Photographs will be taken at the selected sites. One or more most affected body regions, per Investigator's judgement, may be photographed.
- j. The e-Diary will be dispensed to the subject or the e-Diary application will be loaded to the subject's device at Baseline. Collection or removal of application will occur at EOS or at ET/Discon. Subjects enter e-Diary information on a daily basis for their compliance with study treatment starting Baseline/Day 1, recording daily pruritus, daily skin pain NRS, and ADSS starting at Baseline/Day 1.
- k. On Day 1, Day 15, Day 29, Day 57, and Day 85, the study drug will be administered at the study center after all other assessments are performed. All other daily drug intake will be self-administered by the subject, at home, at approximately the same time of the day through Day 112.
- l. PK blood sampling will be done pre-dose on Day 1, Day 15, Day 29 and Day 57.
- m. Tape stripping is only required for subjects in the US and Canada; tape stripping should not be performed for subjects in Poland. Tape strips will be collected from lesional and non-lesional skin pre-dose at Baseline. Tape strip samples will also be collected at the same sites sampled at Baseline on Day 29, Day 57, Day 113, and on Days 141 and 169, if applicable.
- n. Two skin microbiome samples will be collected at Baseline, one from lesional and one non-lesion skin. A skin microbiome sample will also be collected at subsequent visits at the same lesional site sampled at Baseline.
- o. Plasma blood sampling will be done pre-dose.
- p. The immunophenotyping sample is only required for subjects in the US and Canada; immunophenotyping samples should not be collected from subjects in Poland.
- q. Blood sample will be collected from subjects who have consented to participate in the genetic analysis component of the study. Participation is optional. Please see [Section 8.7](#) for further details.

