8.2.4 Clinical Safety Laboratory Assessments

- See [Appendix 11](#) for the list of clinical laboratory tests to be performed and the SoA for the timing and frequency.
- For the three visits requiring fasted labs (Baseline, Day 113, and Day 127), a subject should refrain from eating or drinking (except for water) for a period of at least 8 hours prior to the lab draw.
- The Investigator must review the laboratory report, document this review, and record any clinically relevant changes occurring during the study in the AE section of the CRF. The laboratory reports must be filed with the source documents. Clinically significant abnormal laboratory findings are those that are not associated with the underlying disease, unless judged by the Investigator to be more severe than expected for the subject's condition.
- All laboratory tests with values considered clinically significantly abnormal during participation in the study or within 30 days after the last dose of study treatment should be repeated until the values return to normal or baseline or are no longer considered clinically significant by the Investigator or Medical Monitor.
 - If such values do not return to normal/baseline within a period of time judged reasonable by the Investigator, the etiology should be identified and the Medical Monitor and Sponsor notified.
 - All protocol-required laboratory assessments, as defined in [Appendix 11](#), must be conducted in accordance with the laboratory manual and the SoA.
 - If laboratory values from non-protocol specified laboratory assessments performed at the institution's local laboratory require a change in subject management or are considered clinically significant by the Investigator (e.g., SAE or AE or dose modification), then the results must be recorded in the CRF.

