Appendix 11 Clinical Laboratory Tests

- The tests detailed in [Table 7](#) will be performed by the central laboratory.
- Protocol-specific requirements for inclusion or exclusion of subjects are detailed in [Section 5.0](#) of the protocol.
- Additional tests may be performed at any time during the study as determined necessary by the Investigator or required by local regulations.

Table 7 Protocol-required Safety Laboratory Assessments

Laboratory Assessments	Parameters			
Hematology	Platelet Count	RBC Indices: Mean corpuscular volume (MCV) Mean corpuscular hemoglobin (MCH) %Reticulocytes		White Blood Cell Count with Differential: Neutrophils Lymphocytes Monocytes Eosinophils Basophils
	Red Blood Cell (RBC) Count			
	Hemoglobin			
	Hematocrit			
	White Blood Cell Count			
Clinical Chemistry ^a	Blood Urea Nitrogen	Potassium	Aspartate Aminotransferase (AST)/ Serum Glutamic-Oxaloacetic Transaminase (SGOT)	Total and direct bilirubin
	Creatinine	Sodium	Alanine Aminotransferase (ALT)/ Serum Glutamic-Pyruvic Transaminase (SGPT)	Total Protein
	Glucose [fasting]	Calcium	Alkaline phosphatase	Cholesterol (Total, HDL, LDL) ¹
	Albumin	Chloride	GGT	LDH
	Triglycerides	Uric Acid	Coagulation panel	
Routine Urinalysis	
 • Specific gravity • pH, glucose, protein, blood, ketones, bilirubin, urobilinogen, nitrite, leukocyte esterase by dipstick • Microscopic examination (if blood or protein is abnormal) 			
Other Screening Tests	
 • Follicle-stimulating hormone and estradiol (as needed in women of non-childbearing potential only) • Serum human chorionic gonadotropin (hCG) pregnancy test at screening and urine at baseline and during study (as needed for women of childbearing potential)^b • Serology (HIV antibody, hepatitis B surface antigen [HBsAg], and hepatitis C virus antibody or specify other tests) 			

Laboratory Assessments	Parameters
	
 • Tuberculosis test (PPD or QuantiFERON-TB Gold or T-spot) The results of each test must be entered into the (e)CRF.

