## Appendix I

Visit	Screening		Treatment (Day 1 to Day 113)				Follow-up (Day 127 to Day 169)			
	Day -35 to -1	Day 1	Day 15	Day 29	Day 57	Day 85	Day 113	Day 127/E/T/Discon	Day 141	Day 169
Study Day										
Week Number			Week 2	Week 4	Week 8	Week 12	Week 16	Week 18	Week 20	Week 24
Visit Number	Visit 1	Visit 2	Visit 3	Visit 4	Visit 5	Visit 6	Visit 7	Visit 8	Visit 9	Visit 10
Window (day)			±2	±3	±3	±3	±3	±3	±3	±3
Informed consent	X									
Eligibility check for randomization	X	X								
Medical history	X									
Demographics	X									
Physical examination a	X	X	X	X	X	X	X	X	X	X
Height, weight, and BMI b	X							X		
TB screening	X									
Pregnancy test (females only) c	X	X		X	X	X	X	X		X
COVID-19 test d	X	X								
Clinical laboratory tests e , including FSH at screening f	X	X	X	X	X	X	X	X	X	X
Urinalysis	X	X		X			X	X		
Triplicate 12-lead ECG	X	X		X			X	X		
Vital signs	X	X	X	X	X	X	X	X	X	X
Fitzpatrick skin type	X									
EASI	X	X	X	X	X	X	X	X	X	X
vIGA	X	X	X	X	X	X	X	X	X	X
BSA (palm method to be used for both EASI and SCORAD)	X	X	X	X	X	X	X	X	X	X
Randomization		X								

Visit	Screening	Baseline		Treatment (Day 1 to Day 113)						Follow-up (Day 127 to Day 169)				
		Day 1	Day 15	Day 29	Day 57	Day 85	Day 113	Day 127/E/T/ Discon	Day 141	Day 169				
Study Day	Day -35 to -1													
Week Number	Visit 1		Week 2	Week 4	Week 8	Week 12	Week 16	Week 18	Week 20	Week 24				
Visit Number	Visit 2		Visit 3	Visit 4	Visit 5	Visit 6	Visit 7	Visit 8	Visit 9	Visit 10				
Window (day)			±2	±3	±3	±3	±3	±3	±3	±3				
SCORAD		X	X	X	X	X	X	X	X	X				
Daily Pruritus (PP-NIRS)		X				X								
Daily Skin Pain NRS		X				X								
ADSS		X				X								
Patient Global Assessment (PtGA)		X	X	X	X	X	X	X	X	X				X
DLQI		X	X	X	X	X	X	X	X	X				X
POEM		X	X	X	X	X	X	X	X	X				X
ACQ-5 g		X				X				X				X
Photographs i		X		X	X	X	X	X						X
Provisioning Subject e-Diary Device or Application l		X							X					X
Study drug dosing at study center k		X	X	X	X	X								
Study drug dosing daily at home k		X									X			
Daily subject e-Diary for drug dosing at home		X												
PK sampling – Blood l		X	X	X	X	X	X	X	X	X				
Tape stripping m		X		X	X	X	X	X	X	X				X
Skin microbiome samples (swab) n		X		X	X	X	X	X	X	X				X

Visit	Screening	Baseline			Treatment (Day 1 to Day 113)						Follow-up (Day 127 to Day 169)			

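### Glucose and lipid changes are measured from a fasted baseline, but six of the eight post-baseline laboratory visits have no fasting rule and the SAP does not separate them

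*SAP*

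**What the plan says.** **Collection.** The footnote to the schedule (Protocol 1.3, repeated in SAP Appendix I) reads "Fasting required for labs at Baseline, Day 113 (Week 16), and Day 127/ET/Discon (Week 18". Protocol 8.2.4 gives the same list: "For the three visits requiring fasted labs (Baseline, Day 113, and Day 127". The fast is at least 8 hours. The clinical laboratory row in SAP Appendix I is marked at all ten visits, from Screening to Day 169.

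**Panel.** Protocol Appendix 11, Table 7 puts glucose, triglycerides and cholesterol in the chemistry panel. Glucose is entered as "Glucose [fasting" (the bracket closes there), with no limit by visit. The three-visit fasting footnote is attached to "Cholesterol (Total, HDL, LDL", and not to glucose or triglycerides.

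**Analysis.** SAP VII.D says: "Laboratory data will be summarized using descriptive statistics for the observed and change from baseline by treatment arm and overall". It then adds: "Worst post-baseline CTCAE grade shift from baseline tables will also be provided for hematology, clinical chemistry and urinalysis", limited to tests that have a grading. Tests without a grading go to normal-range shift tables. Protocol 9.4.3 makes clear that change is tabulated visit by visit. Neither document has a fasting flag, filter or separate table.

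**The concern.** The protocol imposes a fast at three visits, so it treats food state as relevant to some of these analytes. The analysis then drops the distinction. A fasted baseline is the reference for visits at which subjects may or may not have eaten. All of those visits also compete to supply the worst post-baseline value.

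At stake is how the metabolic laboratory tables read. Glucose or triglycerides could appear to rise within every arm for a reason unrelated to treatment. A real shift in an active arm would be harder to see against that background, with about 67 subjects per arm.

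**Working it through.** **1. The plan's own count.** Fasted visits: Baseline, Day 113, Day 127 = 3, as Protocol 8.2.4 says. Three places agree on the list (the schedule footnote, 8.2.4 and the Table 7 footnote).

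**2. Visits without a fasting rule.** Laboratory visits in SAP Appendix I: 10. Less Screening and Baseline: 10 − 2 = 8 post-baseline. Less Day 113 and Day 127: 8 − 2 = 6, namely Days 15, 29, 57, 85, 141 and 169 (Weeks 2, 4, 8, 12, 20 and 24).

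**3. What each table compares.**
- Week 16 and Week 18 rows: fasted against fasted.
- The other six rows: uncontrolled food state against fasted.
- Worst post-baseline grade: the worst over both kinds of draw.

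**4. Where visit labels mislead.** SAP VII applies the efficacy windows to safety change from baseline, and SAP IV.C assigns visits by actual study day. A fasted early-termination draw on, say, Day 60 falls in the Week 8 window (Days 43 to 70), beside draws with no fasting rule. An unscheduled draw can fill the Week 16 row if no scheduled one falls in its window. SAP IV.B takes the last non-missing pre-dose value as baseline, so a Screening value, for which no fast is required, can stand in if the Day 1 value is missing.

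**5. Size, under assumptions.** The documents give neither the share of subjects who have eaten (p) nor the shift that eating causes (d, in SD units). I assume p from 25% to 100%, d from 0.25 to 1, within-subject correlation r of 0.5 or 0.8, an upper limit of normal (ULN) at +1.645 SD, and no drug effect.

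- *Mean change* at an unfasted visit is p × d: from 0.25 × 0.25 = 0.06 SD to 1 × 1 = 1.0 SD. At Weeks 16 and 18 it is 0.
- *Spread of change* at such a visit: variance 2(1 − r) + p(1 − p)d². With p = 0.5 and d = 1, r = 0.5 gives 1 + 0.25 = 1.25, so the SD rises by a factor √1.25 = 1.12. With r = 0.8 it is 0.40 + 0.25 = 0.65, a factor √(0.65/0.40) = 1.27. If everyone has eaten (p = 1), a constant shift adds no spread.
- *Worst value above ULN* among subjects normal at baseline (simulation, 300,000 subjects):

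| r | 2 fasted visits | 8 visits, no food effect | 8 visits, d 0.25, p 25% | 8 visits, d 0.5, p 50% | 8 visits, d 1, p 100% |
|---|---|---|---|---|---|
| 0.5 | 7.2% | 19.2% | 21.3% | 29.2% | 59.9% |
| 0.8 | 4.5% | 10.2% | 11.8% | 18.5% | 43.9% |

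The step from the first to the second results column (12.0 and 5.7 percentage points) comes only from taking the worst of eight visits instead of two. Food accounts for what lies beyond the second column: 21.3 − 19.2 = 2.1 to 59.9 − 19.2 = 40.7 points at r = 0.5, and 11.8 − 10.2 = 1.6 to 43.9 − 10.2 = 33.7 points at r = 0.8.

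**6. Between arms.** All arms share one schedule and are randomised 1:1:1:1, so the expected active-minus-placebo difference in mean change is p × d − p × d = 0, and it is likewise 0 for the worst-value share. The standard error of a difference in worst-value share (w) is about √(2w(1 − w)/67). At r = 0.5 it goes from 6.8 points (w = 19.2%) to 7.9 points (w = 29.2%). At r = 0.8 it goes from 5.2 points (w = 10.2%) to 6.7 points (w = 18.5%).

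**The case against.** Much of the case on the other side is sound.

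- *No requirement to fast does not mean fed.* A reader might infer that the plan creates false metabolic worsening in every arm, or that the worst grade will usually come from a fed sample. The documents support neither: they give no share of unfasted subjects and no food effect. Only *can create* is justified.
- *The randomised comparison is protected.* A reader might also infer a bias toward or against the drug. With a common schedule and blinding there is none in expectation, and the placebo column displays any shared shift.
- *Dosing without food restriction is beside the point.* Protocol 5.3.1 concerns how study drug is taken. At the treatment visits with dosing at the center, drug is given after the other assessments, and the schedule states that no blood is drawn post-dose.
- *That the full panel is drawn at every visit is a reading.* The schedule has one laboratory row and does not list analytes by visit. The unrestricted fasting label on glucose could mean that it was intended as a fasting measure throughout. This does not remove the concern: it shows that the label and the three-visit rule disagree. The laboratory manual, which we do not have, may say more.
- *Little depends on these tables.* They are descriptive. No metabolic event is among the events of clinical interest, and Protocol Table 4 has no glucose or lipid criterion. The SAP does not say whether glucose or lipids are among the graded tests.
- *Dropping the other visits would do harm.* Dosing runs through Day 112, so for completers the two post-baseline fasting draws fall one day and about two weeks after the last dose. Tables confined to them would lose every scheduled Week 2 to Week 12 draw.

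What remains is a mismatch of reference in six visit rows and in the worst-value tables, with no rule in the SAP to mark it.

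**Conclusion.** The point holds as a cheap improvement to the SAP, not as a threat to the trial's conclusions. The count is firm: six of eight post-baseline laboratory visits have no fasting rule, and SAP VII.D compares them with a fasted baseline without saying so. The consequence is limited to within-arm readings and added noise in the glucose and lipid tables.

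The size of the distortion is not known. The illustration rests wholly on the assumed shift, share unfasted, correlation and normal limit. At its low end the effect is negligible; at its high end it would dominate the shift tables. It also assumes that the whole chemistry panel is drawn at each visit marked in the schedule.

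**What to change.** In SAP VII.D, for glucose, triglycerides and cholesterol:

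1. Base the main change-from-baseline and worst-shift tables on protocol-fasted draws: Baseline, Day 113 and Day 127/early termination. Select on the fasting draw itself, not only on the analysis-window label. The documents do not say whether actual fasting status is recorded; if it is not, select on the nominal visit at collection.
2. Keep the remaining visits in separate summaries by arm, labelled *fasting status not controlled* and read against placebo, so that on-treatment changes at Weeks 2 to 12 stay visible.
3. State how a Screening value that serves as baseline is handled in these tables.

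In the protocol, reconcile the unrestricted fasting label on glucose in Table 7 with the three-visit fasting rule, and make clear which analytes the Table 7 footnote covers.

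For the SAP the cost is one or two sentences, a programming filter and an additional set of tables. The fasting tables will hold only two post-baseline visits. No data are discarded.
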